6.2.2 Group 2 (Multiple Dose Cohort)

Table 4: Group 2 Gel Schedule

Gel	Visit	Visit Name	Number of doses dispensed	Location of use	Timing of final dose of gel relative to coitus
	1	Screening (Baseline CVL)			
	2	Enrollment- Provision of Study Product	7**	1 Clinic 5 Home	
-1 hr	3a	Gel -1/Coitus	1	1 Hotel or comparable location	-1 hr
	3b	Post-Coital Sampling			
	4	Provision of Study Product	7**	1 Clinic 5 Home	
	5	Sampling*	1	1 Clinic	
-72 hr	6	Provision of Study Product	8**	1 Clinic 6 Home	
	7a	Gel -72/Coitus			-72 hr
	7b	Post-Coital Sampling			
	8	Provision of Study Product	8**	1 Clinic 6 Home	
	9/ Final	Sampling*			

*The collection of samples should be matched to the collection of samples of the preceding gel/coitus visit timing.

**Participants will be given one extra dose, see Section 6.5 for additional details.

At Visit 2 (Enrollment/ Provision of Study Product) while in the clinic, the female participant will vaginally administer the content of one applicator of tenofovir 1% gel. For the next five consecutive days she will vaginally insert the content of one applicator of tenofovir 1% gel daily at home (i.e., doses 2-6). Doses should be inserted at approximately the same time each day. At Visit 3a (Gel -1hr/Coitus) the couple will return to the clinic to review procedures and the female participant will insert into the vagina the content of one applicator of tenofovir 1% gel (i.e., the 7th dose) at the location where coitus is to occur (hotel or comparable site). This dose should be applied approximately 1 hour prior to coitus. Following a minimum washout period of 20 days to allow for clearance of any residual drug and to provide time for the participant's menstrual period, the female participant will return to the clinic for Visit 4 (Provision of Product) and insert into the vagina the content of one applicator of tenofovir 1% gel. For the next five consecutive days she will insert into the vagina the content of one applicator of tenofovir 1% gel daily at home (i.e., doses 2-6). Doses should be inserted at approximately the same time each day. At Visit 5 (Sampling) the participant will return to the clinic and insert into the vagina the content of one applicator of tenofovir 1% gel (i.e., 7th dose).

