7.4 Group 2 (Multiple Dose Cohort)- Screening Visit (Visit 1)

A Screening Visit may take place up to 30 days prior to the Enrollment Visit. Multiple visits may be conducted to complete all required screening procedures, if necessary. Written informed consent for screening will be obtained before any screening procedures are initiated. Both the female and the male must meet the eligibility requirements for the couple to be eligible. For participants who do not meet the eligibility criteria (e.g., STI or HIV-positive, self-reported non-monogamy, etc.), screening will be discontinued for the couple once ineligibility is determined.

All test results will be provided to an individual participant in a private room to ensure participant confidentiality. If a participant is found to be ineligible based upon STI or HIV status study staff will not inform the infected participant's partner. Participants may choose to disclose this information on their own. Study staff will comply with local requirements to report communicable diseases including HIV-1 identified among study participants to health authorities.

In addition, if one partner admits to non-monogamy, study staff will inform the couple that they are ineligible for the study; however non-monogamy will not be disclosed to the couple as the reason for ineligibility.

All individuals who come to the clinic for Screening will be provided counseling regarding HIV/STI prevention, see Table 11. Participants will be informed that condoms are the only known way to prevent HIV and other STIs.

Note: Participants may rescreen a total of one time; however both the female and male participants must meet the eligibility requirements at the time of the screening.

Table 10: Group 2- Multiple Dose Cohort Study Visit Schedule

Group 2- Multiple Dose Cohort				
Gel	Visit	Visit Name	Targeted Visit Schedule	Coitus
	1 ♂♀	Screening (Baseline CVL)		
	2 ♂♀	Enrollment- Provision of Study Product	To occur ~2-3 days following the final day of the female participant's period*	
-1 hr	3a ♂♀	Gel -1/Coitus	To occur 6 days after Visit 2	X
	3b ♀	Post-Coital Sampling	To occur ~2 hrs after coitus	
	4 ♀	Provision of Study Product	To occur after a min. 20 day washout period	
	5 ♀	Sampling	To occur at similar time relative to sampling at Visit 3b	
-72 hr	6 ♀	Provision of Study Product	To occur after a min. 20 day washout period	
	7a ♂♀	Gel -72/Coitus	To occur 9 days after Visit 6	X
	7b ♀	Post-Coital Sampling	To occur ~2 hrs after coitus	

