At Visit 7a (Gel -72/Coitus), following a 7-day regimen of product, couples will return to the clinic to engage in coitus approximately 72 hours after the female participant's last dose of product. Again, prior to the coital visit, participants will receive coital visit instructions, these instructions will include information regarding when participants should return to the study clinic (not to exceed 2 hours after completing the coital act), and other information to ensure participants comply with study requirements. Participants will then engage in coitus and female participants will return to the clinic undergo post-coital sampling procedures at Visit 7b (Post-Coital Sampling).

After a minimum 20 day washout period, the female participant will return to the clinic for Visit 8 (Provision of Study Product), she will apply the first of the 7 daily doses of gel at the clinic and receive a study product provision sufficient to allow for the next 6 daily doses at home (doses 2-7).

At Visit 9 (Sampling), the couple returns the clinic after the female participant has administered the final dose of gel approximately 72 hours prior to the visit. Participants will return to the clinic and the female participant will undergo sampling procedures for the final time.

Table 12: Group 2- Visit 2: Enrollment- Provision of Study Product, Visit 4: Provision of Study Product, Visit 6: Provision of Study Product, Visit 8: Provision of Study Product

Group 2 Visit 2- Enrollment: Provision of Study Product, Visit 4: Provision of Study Product, Visit 6: Provision of Study Product, Visit 8: Provision of Study Product			
Component	Female Participants	Male Participants	
Administrative and Regulatory	
 Assess eligibility Δ Eligibility confirmationΔ Eligibility to continue study participation, including continued monogamy◇ Update locator information Provide reimbursement Schedule next visit, if indicated 	
 Assess eligibility Δ Eligibility confirmationΔ Update locator informationΔ Provide reimbursementΔ Schedule next visit, if indicatedΔ 	

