8 ASSESSMENT OF SAFETY

8.1 Safety Monitoring

Site IoRs are responsible for continuous close safety monitoring of all study participants, and for alerting the Protocol Team if unexpected concerns arise. A sub-group of the Protocol Team, including the Protocol Chair, DAIDS Medical Officer (MO), Protocol Safety Physicians, CONRAD Safety Physicians, and SCHARP Clinical Affairs Safety Associates will serve as the PSRT. The MTN Statistical Data Management Center (SDMC) prepares routine AE and clinical data reports for review by the PSRT, which meets via conference call approximately once per month or as needed throughout the period of study implementation to review safety data, discuss product use management, and address any potential safety concerns. The content, format, and frequency of the safety data reports will be agreed upon by the PSRT and the SDMC in advance of study implementation.

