8.3 Adverse Events Definitions and Reporting Requirements

8.3.1 Adverse Events

An AE is defined as any untoward medical occurrence in a clinical research participant exposed to an investigational product and which does not necessarily have a causal relationship with the investigational product. As such, an AE can be an unfavorable or unintended sign (including an abnormal finding, for example), symptom or disease temporally associated with the use of an investigational product, whether or not considered related to the product. This definition is applied to all study groups, and is applied to all enrolled participants beginning at the time of eligibility checklist completion and final sign-off. The term “investigational product” for this study refers to all study products, see Section 8.4.2.

Study participants will be provided instructions for contacting the study site to report any untoward medical occurrences they may experience. In cases of potentially life-threatening events, participants will be instructed to seek immediate emergency care. Where feasible and medically appropriate, participants will be encouraged to seek evaluation where a study clinician is based, and to request that the clinician be contacted upon their arrival. With appropriate permission of the participant, whenever possible, records from all non-study medical providers related to untoward medical occurrences will be obtained and required data elements will be recorded on study CRFs. All participants reporting an untoward medical occurrence will be followed clinically until the occurrence resolves (returns to baseline) or stabilizes.

Study site staff will document in source documents all AEs reported by or observed in enrolled study participants regardless of severity and presumed relationship to study product. Study staff also will report on CRFs the following subset of AEs reported by or observed in enrolled participants:

- All genital, genitourinary, and reproductive system AEs
 - Fetal losses (e.g., spontaneous abortions, spontaneous fetal deaths, stillbirths) will not be reported as AEs. However, untoward maternal conditions that either result in or result from fetal losses are reported as reproductive system AEs
 - Genital bleeding clinically assessed to be expected is not an AE
- All AEs of severity Grade 2 or higher
- All serious AEs, as defined by the International Conference on Harmonization Consolidated Guidance for Good Clinical Practice

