Treatment or prescribe treatment for UTI/RTI/STIs or refer	*	*	*		*		*	*		*	*
Record/update AEs (FEMALE ONLY)			X	X	X	X	X	X	X	X	X
Record/update AEs (MALE ONLY)											X
Semen sample (MALE ONLY)	X										
Behavioral/Counseling											
Conduct behavioral assessment		X		X		X			X		X
Conduct acceptability assessment											X
Product adherence assessment				X		X			X		
Provide HIV pre-post- test counseling	X										X
Provide full/modified HIV/STI risk reduction counseling	X	X	X		X		X	X		X	X
Provide adherence counseling		X	X		X		X	X		X	

	Visit 1	Visit 2	Visit 3a	Visit 3b	Visit 4	Visit 5	Visit 6	Visit 7a	Visit 7b	Visit 8	Visit 9
	SCR	ENR	Gel -1/Sex	Post Coital Sampling (♀)	Provision of Product (♀)	Sampling (♀)	Provision of Product (♀)	Gel -72/Sex	Post Coital Sampling (♀)	Provision of Product (♀)	Sampling/ Final Clinic
(FEMALE ONLY)											
Provide contraceptive counseling (FEMALE ONLY)	X	X	X		X	X	X	X		X	
Laboratory											
hCG (FEMALE ONLY)	X	X	X		X	X	X	X		X	X
Urine culture	*	*	*		*		*	*		*	*
Urine NAAT for GC/CT	X	*	*		*		*	*		*	*
CBC with platelets (FEMALE ONLY)	X										
HIV-1 serology	X										X
PK- blood (FEMALE ONLY)				X		X			X		X
Syphilis serology	X										
HBsAg	X										
Plasma archive		X									
CVL for PK, PD, and/or semen biomarker (FEMALE ONLY)	X			X		X			X		X
Vaginal fluid pH (FEMALE ONLY)	X	X	X	X	X	X	X	X	X	X	X
Vaginal and cervical biopsies (FEMALE ONLY)				X		X			X		X
Cervical cytobrush (FEMALE ONLY)				X		X			X		X
Rapid Trichomonas test (FEMALE ONLY)	X	*	*		*		*	*		*	*
KOH wet mount for candidiasis (FEMALE ONLY)	*	*	*		*		*	*		*	*
Wet mount for BV (FEMALE ONLY)	*	*	*		*		*	*		*	*
Cervical specimen for pap smear (FEMALE ONLY)	*										
Rectal sponge for PK (FEMALE ONLY)				X		X			X		X
Study Product											
Provision of study product		X	X		X		X	X		X	
Collect all used applicators/unused study product			X	X		X		X	X		X
Study product use instructions		X	X		X		X	X		X	

X required procedure, * if indicated, ♀= Female participants only

Note: At the Final Visit, participants should receive available test results, however if results are not available study staff should make arrangement to disclose those results

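### Men's adverse events are scheduled for recording only at the final visit, although men attend earlier visits after first gel exposure and before re-exposure

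*Protocol*

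**What the plan says.** Appendix II splits AE recording by sex. The row "Record/update AEs (FEMALE ONLY" is marked at every visit from 3a to 9, and the row "Record/update AEs (MALE ONLY" at Visit 9 alone. The procedure tables agree: Table 13 (Visits 3a and 7a) lists AE recording for women but not for men, and Table 15 (Visit 9) lists it for both.

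In Group 1, Table 7 lists no AE recording at the 'a' visits for either sex. Women have it at the sampling visits 2b to 6b (Table 8), which men do not attend. Men's only entry is at Visit 7b (Table 9). Appendix I shows the same pattern.

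Men do attend in between. For Group 2 Visit 7a, Section 7.5 says "couples will return to the clinic to engage in coitus approximately 72 hours after the female participant's last dose of product". At that visit (Table 13), and at Group 1 Visits 5a and 7a (Table 7), men have medical history and medications updated and a modified physical examination, with a genital examination if indicated.

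On coverage, Section 8.3.1 says that the AE definition "is applied to all enrolled participants beginning at the time of eligibility checklist completion and final sign-off". Section 8.1 adds: "Site IoRs are responsible for continuous close safety monitoring of all study participants". Section 8.3.1 also sends every genital AE to the case report form, whatever its grade.

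**The concern.** Men are exposed to gel through unprotected coitus. In Group 2 the first occasion follows the seventh dose at Visit 3a, for which Section 6.2.2 says "This dose should be applied approximately 1 hour prior to coitus". A second coital session follows at Visit 7a. In Group 1 the gel sessions are at Visits 3a, 5a and 7a. On the schedule, a man goes into each later session without a scheduled AE entry, although he has just been seen in the clinic.

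The male effects that the protocol leads one to expect are mild and local: Section 13.4.1 gives mild pain and itching as the most common findings in the male tolerance study. Events of that kind must go on the case report form under Section 8.3.1, yet a man might not mention them unless asked. At stake is the completeness and timing of male safety recording between first exposure and the final visit. Safety is not a primary, secondary or exploratory endpoint in Section 10.2.

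**Working it through.** The protocol gives no figure for this interval, so the visit days are built from its minimum spacing.

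**Group 2 inputs**
- Table 10, Visit 3a: "To occur 6 days after Visit 2".
- Table 10, Visit 7a: "To occur 9 days after Visit 6".
- Table 10: at least 20 days of washout before Visits 4, 6 and 8.
- Section 6.2.2: dose 1 at Visit 4, doses 2 to 6 on the next five days and dose 7 at Visit 5, so Visit 5 is 6 days after Visit 4.
- Assumption: Visit 9 is 9 days after Visit 8, as Visit 7a is after Visit 6. Both follow seven daily doses and a 72-hour wait.

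**Group 2 days, with Visit 2 as day 0**
- Visit 3a: day 6 (first male exposure)
- Visit 4: 6 + 20 = 26
- Visit 5: 26 + 6 = 32
- Visit 6: 32 + 20 = 52
- Last dose of that course: 52 + 6 = 58
- Visit 7a: 52 + 9 = 61
- Visit 8: 58 + 20 = 78 if washout runs from the last dose, or 61 + 20 = 81 if it runs from Visit 7
- Visit 9: 78 + 9 = 87, or 81 + 9 = 90

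The minimum total of 87 to 90 days (12.4 to 12.9 weeks) is compatible with the stated follow-up of about 14 weeks.

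**Group 2 gaps**
- First exposure to the only scheduled male AE record: 87 − 6 = 81 days, or 90 − 6 = 84 days (11.6 to 12.0 weeks).
- If follow-up lasts the full 14 weeks: 98 − 6 = 92 days.
- First exposure to Visit 7a, the next visit that men attend: 61 − 6 = 55 days (7.9 weeks).
- Visit 7a to Visit 9: 87 − 61 = 26 days, or 90 − 61 = 29 days.

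**Group 1 inputs (Table 5)**
- Visit 3a is about 3 to 7 days after Visit 2.
- At least 10 days of washout precede each of Visits 4a, 5a, 6a and 7a.
- Sampling at 5b and 6b falls about a day after dosing, because the dose precedes coitus or its matched time by about 24 hours.

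**Group 1 gaps, counted from Visit 3a**
- To Visit 5a: 10 + 10 = 20 days.
- To Visit 7, washout counted from the dosing visit: 4 × 10 = 40 days.
- To Visit 7, washout counted from sampling at 5b and 6b: 40 + 1 + 1 = 42 days.

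**Sessions before the first scheduled male record**
- Group 2: two (Visits 3a and 7a).
- Group 1: three (Visits 3a, 5a and 7a), the last shortly before the recording at 7b.

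In both groups, a visit that men already attend falls before re-exposure and carries a history update and an examination but no AE line.

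**The case against.** A reader might infer that male safety data as a whole reach the monthly safety review weeks late, rest on recall and are under-reported. The documents do not support that. Section 8.3.1 does not tie AE capture to the visit grid. Staff must document any AE that a participant reports or that they observe, and every genital AE goes on the case report form. Participants are told how to report events, and Section 7.7 allows interim visits for them. Section 8.2 provides ongoing review of incoming safety data and ad hoc meetings of the safety team as well as monthly ones. The history update and examination before re-exposure can also bring events to light, and these then fall under Section 8.3.1. No figure in the protocol bears on under-reporting.

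A reader might also infer that the schedule contradicts Section 8.3.1. It does not: that section says who is covered and from when, and sets no visits at which events must be solicited. Section 8.1 states an investigator's duty and fixes no schedule. The tables and appendices agree with one another.

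Lighter follow-up of men also has some stated basis. Section 2.5.1 reports that seven days of direct penile application were well tolerated, and judges significant toxicity in male partners unlikely. The later sessions are not all alike either. At Group 1 Visit 5a and Group 2 Visit 7a, coitus follows the last dose by about 24 and 72 hours, so exposure is to residual gel. In the single-dose study cited there, vaginal fluid levels were generally 1.5 to 5.0 × 10⁶ ng/mL through 8 hours and 4.5 to 47.1 × 10⁴ ng/mL at 24 hours.

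All of this stands, and it narrows the point. One thing remains: women have the same spontaneous-reporting routes and are still given scheduled AE recording throughout, and the schedule gives no reason for omitting it for men at visits they already attend.

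**Conclusion.** The point holds in a narrow form. Routine AE recording for men is scheduled only at the final visit in both groups, and is absent from the visits that men attend between first exposure and re-exposure. What may be missed or recorded late is an event that the man does not volunteer and that the history update and examination do not reveal. For such an event, the first scheduled record comes 81 to 84 days after first exposure in Group 2 and 40 to 42 days in Group 1.

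These figures rest on minimum intervals, on Visit 9 falling 9 days after Visit 8, and on washout running from either the last dose or the preceding visit. Longer actual spacing would lengthen them. The PK and PD analyses are unaffected. This is a low-priority improvement to a stated schedule and does not show a failure of safety oversight.

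**What to change.** Add the AE recording line for men at Visits 5a and 7a in Group 1 (Table 7 and Appendix I) and at Visit 7a in Group 2 (Table 13 and Appendix II), next to the history update already listed. Visit 3a does not need it for this purpose, because at that clinic visit men have not yet been exposed to gel.

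The wait for a first scheduled record after first exposure then falls to about 20 days in Group 1 and 55 days in Group 2, and a record is taken before each re-exposure. The Group 2 wait is still nearly eight weeks, because men attend no visit between 3a and 7a, so spontaneous reporting remains the main route in that interval.

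The cost is one form line at existing visits, with no new visit, procedure or sample.

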At Visit 6 (Provision of Product) while in the clinic, the female participant will vaginally administer the content of one applicator of tenofovir 1% gel. For the next six consecutive days she will vaginally insert the content of one applicator of tenofovir 1% gel daily at home (i.e., doses 2-7). Doses should be inserted at approximately the same time each day. Approximately 72 hours after the administration of the last vaginal dose, couples will return to the clinic for Visit 7a (Gel -72/Coitus). Following a minimum washout period of 20 days to allow for clearance of any residual drug and to provide time for the participant's menstrual period, the female participant will return to the clinic for Visit 8 (Provision of Product) and insert into the vagina the content of one applicator of tenofovir 1% gel. For the next six consecutive days she will insert into the vagina the content of one applicator of tenofovir 1% gel daily at home (i.e., doses 2-7). Doses should be inserted at approximately the same time each day. The final dose of gel should be administered approximately 72 hours prior to Visit 9/Final (Sampling).

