6.5 Study Product Dispensing

Study products are dispensed by the site pharmacy to the study staff on behalf of enrolled participants, upon receipt of a written prescription from an authorized prescriber. An authorized prescriber includes the IoR or a licensed clinician directly responsible to the IoR as noted on the FDA 1572 Form.

For both Group 1 and 2, the doses that will be administered in the clinic will be dispensed on the day of the clinic visit. The dose in Group 1 and Group 2 that is to be self-administered at the hotel (or comparable site) just prior to coitus will be dispensed on that day at the clinic. Group 2 participants will receive 6 pre-filled applicators of tenofovir 1% gel at the clinic visit just prior to each of the at home administration periods at Visit 2 and Visit 4. This will provide applicators for doses 2-6 and one extra should an applicator become unusable for any reason. Group 2 participants will receive 7 pre-filled applicators of tenofovir 1% gel at the clinic visit just prior to each of the at home administration periods at Visit 6 and Visit 8. This will provide participants with applicators for doses 2-7. This will provide one extra dose should an applicator become unusable for any reason.

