7 STUDY PROCEDURES

An overview of the study visit and evaluations schedule is presented in Appendices I and II. Presented in this section is additional information on visit-specific study procedures. Detailed instructions to guide and standardize procedures across sites are provided in the MTN-011 SSP Manual available at www.mtnstopshiv.org/.

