Clinical	
 Review/update medical and menstrual history Review/update concomitant medications Disclose available test results Offer panty liners Perform a modified physical examination Δ Record/update AEs◇ Perform pelvic examΔ, if indicated Treat or prescribe treatment for UTI/RTI/STIs or refer, if indicated 	
 Review/update medical historyΔ Review/update concomitant medicationsΔ Disclose available test resultsΔ Perform a modified physical examination Δ Perform genital examΔ Treat or prescribe treatment for UTI/RTI/STIs or refer, if indicatedΔ 	
Behavioral/ Counseling	
 Conduct behavioral assessmentΔ Provide contraceptive counseling Provide modified HIV/STI risk reduction counseling Provide adherence counseling 	
 Conduct behavioral assessmentΔ Provide modified HIV/STI risk reduction counseling Δ 	
Laboratory	Urine	
 hCG Urine NAAT for GC/CT, if indicated Urine culture, if indicated 	
	Vaginal/ Cervical	
 Vaginal fluid pH Rapid Trichomonas test, if indicated KOH wet mount for candidiasis, if indicated Wet mount for BV, if indicated 	
	Blood	
 Plasma archiveΔ 	
 Plasma archiveΔ
Study Product Supply	
 Provision of study product Study product use instructions 		

Δ To be collected at Visit 2 only, ◇=Visits 4, 6, and 8

Table 13: Group 2- Visit 3a: Gel -1/Coitus, Visit 7a: Gel -72/Coitus

Group 2 Visit 3a: Gel -1/Coitus, Visit 7a: Gel -72/Coitus Male and Female Procedures		
Component	Female Participants	Male Participants
Administrative and Regulatory	
 Eligibility to continue study participation, including continued monogamy Update locator information Provision of coitus visit instructions Provide reimbursement Schedule next visit or contact, if indicated 	
 Eligibility to continue study participation, including continued monogamy Update locator information Provide reimbursement Schedule next visit or contact, if indicated Provision of coitus visit instructions

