	Vaginal/Cervical	
 Vaginal fluid pH CVL 
 PK PD Semen biomarker Vaginal and cervical biopsies 
 PK Cervical cytobrush 
 PK

	Rectal	
 Rectal Sponge 
 PK
Study Product Supply		
 Collect all used applicators/unused study product

■ To be performed at Visit 3b and 7b only. ◇= Visit 5 only

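### Group 2 schedule tables supply gel at Visit 7a, where none is due, and omit it at Visit 5, where the seventh dose is given

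*Protocol*

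**What the plan says.** Two sets of statements in the Protocol describe when Group 2 women are given gel.

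**Schedule tables.** The Group 2 schedule in Appendix II has a row "Provision of study product" marked at Visits 2, 3a, 4, 6, 7a and 8. The cell for Visit 5 is empty. The legend defines the mark as "X required procedure". The row for product-use instructions has the same pattern. In Section 7.5, one procedure table serves two visits, under the caption "Table 13: Group 2- Visit 3a: Gel -1/Coitus, Visit 7a: Gel -72/Coitus". It lists product provision and use instructions with no limit to one of the two visits. Table 14 covers Visits 3b, 5 and 7b, and its product entry is only "Collect all used applicators/unused study product".

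**Dosing text.** Section 6.2.2 says "At Visit 5 (Sampling) the participant will return to the clinic and insert into the vagina the content of one applicator", and identifies this as the seventh dose. For the later course it says "Approximately 72 hours after the administration of the last vaginal dose, couples will return to the clinic for Visit 7a". Table 4 agrees: one dose is dispensed at Visit 5 for clinic use, and the dispensing and location cells for Visit 7a are blank. The narrative in Section 7.5 and the design summary in Section 10.1 place the doses in the same way. Section 6.5 adds that "the doses that will be administered in the clinic will be dispensed on the day of the clinic visit", so the Visit 5 dose has to be supplied at Visit 5.

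**The concern.** The two descriptions cannot both be followed. Visit 5 is the gel-without-coitus control at -1 hour, and Visit 7a opens the gel-with-coitus condition at -72 hours. Each is one half of a within-woman pair in the primary PK and PD analyses of Section 10.6.2.

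A site working from the visit-procedure lists could hand out gel at Visit 7a. If it were used, the 72-hour interval that defines that condition would be lost. The same site could fail to supply the dose at Visit 5. Sampling there is meant to match Visit 3b, roughly 3 hours after gel (1 hour before coitus plus 2 hours after). Without the seventh dose it would fall about a day after the sixth.

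The single-dose data in Section 2.5.1 give an idea of scale. Mean vaginal tissue tenofovir was 186 and 89 (x10^3 ng/g) at 2 and 4 hours, against 15 at 24 hours, a ratio of 186/15 = 12.4 or 89/15 = 5.9. Repeated dosing may change that ratio, but the study is designed to detect a 25% difference (Section 10.4.1).

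**Working it through.** The Protocol states no figure for this point, so the check sets the tables side by side and counts.

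**Step 1: visits at which gel is supplied.** Appendix II has 11 visit columns (1, 2, 3a, 3b, 4, 5, 6, 7a, 7b, 8, 9).

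| Visit | Table 4 and dosing text | Appendix II | Tables 12 to 14 |
|---|---|---|---|
| 2 | yes | yes | yes (Table 12) |
| 3a | yes | yes | yes (Table 13) |
| 4 | yes | yes | yes (Table 12) |
| 5 | **yes** | **no** | **no** (Table 14) |
| 6 | yes | yes | yes (Table 12) |
| 7a | **no** | **yes** | **yes** (Table 13) |
| 8 | yes | yes | yes (Table 12) |

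The dosing visits are {2, 3a, 4, 5, 6, 8} and the Appendix II provision visits are {2, 3a, 4, 6, 7a, 8}. Omitted: {5}. Added: {7a}.

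**Step 2: doses per course (clinic start + home + final visit).**

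- Visits 4 to 5, dosing text: 1 + 5 + 1 = 7.
- Visits 4 to 5, schedule tables read literally: 1 + 5 + 0 = 6.
- Visits 6 to 7a, dosing text: 1 + 6 + 0 = 7.
- Visits 6 to 7a, schedule tables read literally: 1 + 6 = 7, plus a further provision at Visit 7a when no dose is due.

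The spare applicator handed out at Visit 4 does not close the gap. Section 6.5 provides it in case an applicator becomes unusable, and Table 4 shows a separate dose for Visit 5.

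**Step 3: is it a text-extraction artefact?** Two Appendix II rows and two procedure tables show the same pattern. Some in-body marks in Table 14 are lost, but its product entry has no provision line to which a Visit 5 mark could attach. No legend is visible for Table 13. The corresponding row in Appendix I for Group 1 (Visits 3a, 4a, 5a, 6a, 7a) matches Table 3 exactly, including the no-coitus dosing visits. The error is confined to Group 2.

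**Step 4: would the evaluability rule catch it?** Section 10.5 requires gel on at least 5 of the 7 days before the study visit.

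- Visit 5 is day 6, with Visit 4 as day 0. The seven prior days are days -1 to 5, and doses fall on days 0 to 5. That is 6 of 7, whether or not the day 6 dose is given.
- Visit 7a is day 9, with Visit 6 as day 0 (Table 10). The seven prior days are days 2 to 8. Doses fall on days 0 to 6, of which days 2 to 6 are in the window. That is 5 of 7, whether or not gel is used on day 9.

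If the rule is read instead as 5 of the 7 course doses, a missed Visit 5 dose leaves 6 of 7 and extra gel at Visit 7a leaves 7 of 7. The couple passes under either reading.

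**The case against.** The strongest reply is that this is clerical. Every place that specifies the regimen agrees: Table 4, Section 6.2.2, the Section 7.5 narrative and Section 10.1. The narrative comes just before Tables 13 and 14, and the name of Visit 7a carries the -72 hour interval. Dispensing needs a written prescription. Section 7 describes the appendices only as a summary ("An overview of the study visit and evaluations schedule is presented in Appendices I and II") and refers sites to a procedures manual not available here. Provision is also not insertion: no table tells a woman to use gel at Visit 7a or to skip the dose at Visit 5. Finally, the 5-of-7 rule is an adherence minimum and was never meant to check dosing on the visit day.

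Most of this stands, and it limits the point. Misdosing would need a site to follow the table against explicit text. The evaluability count is not a consequence of the schedule error; it shows only that the rule is no backstop. Applicator collection and the adherence assessment might still record a deviation.

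The reply does not remove the contradiction. Tables 13 and 14 are the visit-procedure lists in Section 7.5 itself, so the description of the appendices as an overview does not cover them. The unseen manual cannot be assumed to correct them.

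**Conclusion.** The Protocol contradicts itself on gel supply at two Group 2 visits. Of six dosing visits, one (Visit 5) is missing from the schedule and procedure tables, and one non-dosing visit (Visit 7a) is added. Two of the four Group 2 sampling conditions are touched, each one side of a primary pair.

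The tables are wrong and the dosing text is right: the text is consistent throughout, gives seven doses in each course, and fits the visit names. The harm is a risk of misdosing, not an expected outcome, and no analysis or sample-size figure changes. The visit-day counts assume Visit 5 falls six days after Visit 4 (seven consecutive daily doses) and Visit 7a nine days after Visit 6. The direct contradiction concerns provision; the use-instructions row follows it.

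**What to change.** - **Table 13:** limit product provision and product-use instructions to Visit 3a.
- **Table 14:** add both items for Visit 5 only.
- **Appendix II, Group 2:** in both rows, move the mark from Visit 7a to Visit 5, so that they read Visits 2, 3a, 4, 5, 6 and 8.
- **Sites:** issue a clarification memo.

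Both courses then show seven doses (1 + 5 + 1 and 1 + 6 + 0), in line with Table 4. The adherence-counselling and panty-liner rows in Appendix II also have a mark at Visit 7a and none at Visit 5; they could be reviewed in the same edit, but this is optional.

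The cost is a table correction and a memo, with no effect on enrolment or analysis.
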